3.9.3 Criteria for discontinuation of investigational product during the second year extension period:

Criteria for discontinuing investigational product at Week 52:

Subjects not meeting the criteria to continue in the second year extension will not receive any IP at Week 52 and will complete the study after completing the required follow-up visits.

Subjects meeting the following criteria may continue to receive blinded IP between Weeks 52 and 100.

- (i) Meeting all of the following criteria based on the renal portion of the PRR definition:
 - eGFR is:
 - ≥ 60 mL/min/1.73 m² or no confirmed decrease of eGFR from baseline of $\geq 20\%$
 - Improvement in 24-hour UPCR:
 - For subjects with a baseline UPCR ≤ 3 mg/mg: <1.0 mg/mg
 - For subjects with a baseline UPCR >3 mg/mg: $>50\%$ improvement from baseline and ≤ 3.0 mg/mg

Renal discontinuation criteria must be confirmed in two separate samples. The second measurement should be at least 1 week after the first measurement.

- (ii) No discontinuation of IP
- (iii) Negative HIV test after signing the Main ICF

Criteria for discontinuing investigational product at Week 52, Week 56 or Week 60

- Failure to obtain Pap smear after Week 48 with result available at Week 60 at latest
- Pap smear result not meeting the eligibility criteria (see [Appendix K](#)) at Week 52, 56, or 60 of a Pap smear obtained after Week 48
- Failure to obtain Week 52 QuantiFERON test result by Week 56

Criteria for discontinuing investigational product at Week 60 and later

- OCS >7.5 mg/day (except one OCS burst and taper)
- MMF >2 gm/day or >Week 52 dose, if Week 52 dose <2 gm/day

Subjects who discontinue the IP during the second year extension period will be followed until Week 104 (or for a minimum of 12 weeks after last dose of IP for subjects for whom IP was discontinued within 12 weeks of Week 104).

3.9.4 Criteria for discontinuation of investigational product for reasons other than lack of efficacy at any time during the study

Subjects may be discontinued from IP in the following situations:

1. Subject decision: The subject is at any time free to discontinue treatment, without prejudice to further treatment. The primary reason should be documented as one of the following:
 - (a) Subject is unable to comply with protocol-specified visits and/or procedures due to conflicts not related to clinical study
 - (b) An AE or laboratory abnormality is of concern to the subject, but not clinically significant to physician

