8.5.4 Analysis of safety variables

Adverse events (including AESIs) will be summarised by means of counts summaries by Medical Dictionary for Regulatory Activities (MedDRA) System Organ Class and Preferred Term separately for the study periods (treatment period and follow-up period). All AEs will be listed.

Laboratory data for haematology and clinical chemistry will be summarised. The frequency of changes with respect to normal ranges between baseline and each post-treatment time point will be tabulated. Frequencies of clinically noteworthy values (defined in the SAP) occurring during the clinical study will also be given. Shifts from normal to abnormal between baseline and each post baseline time point will be evaluated for urinalysis.

The incidence of markedly abnormal values and changes from baseline in the ECG parameters will be summarised by treatment group.

The proportion of subjects with suicidal behaviour and suicidal ideation throughout the study based on the C-SSRS will be presented for each treatment group. The proportion of subjects within each of the 4 suicidal behaviour categories and within each of the 5 suicidal ideation sub-categories will also be presented for each treatment group. Descriptive statistics on the total number of attempts, total number of interrupted attempts, and total number of aborted attempts will be summarised for each treatment group.

SLEDAI-2K based Flare Assessment Instrument to capture extra-renal flares: The SLEDAI 2K based Flare Assessment Instrument has 2 sets of definitions: one for severe and one for mild/moderate flares. For the purpose of assessing extra-renal flares the renal components will not be considered for the SLEDAI 2K score. SLEDAI-2K based Flare will be summarised as appropriate.

Other safety variables will be summarised as appropriate. Further details are provided in the SAP.

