1.2 Study design

This is a Phase 2, multi-centre, multinational, randomised, double-blind (prior to the primary analysis), placebo-controlled study to evaluate the efficacy and safety of two IV treatment regimens of anifrolumab versus placebo, while taking protocol-specified SOC treatment with mycophenolate mofetil (MMF) and corticosteroids, in subjects with active biopsy-proven proliferative LN. The study will be performed in adult subjects, 18 to 70 years of age. The study duration is approximately 116 weeks (including screening, treatment and follow-up periods) for those subjects who meet the criteria for the second year extension period and approximately 64 weeks for those subjects who do not meet the criteria for the second year extension period.

[figure not shown]
In this study, approximately 150 subjects will be randomised in a 1:1:1 ratio to receive one of two IV anifrolumab dosing regimens or placebo, which will continue until Week 52, as follows:

- **Basic Regimen:** Anifrolumab 300 mg IV Q4W for 13 doses plus SOC or

- **Intensified Regimen:** Anifrolumab 900 mg IV Q4W for the first 3 doses followed by 300 mg IV Q4W for 10 doses plus SOC or
- **Placebo:** IV Q4W plus SOC

The primary objective will be evaluated at Week 52. After Week 52, eligible subjects will continue with their randomised treatment plus SOC until Week 104. Those subjects not eligible to continue with treatment based on the Week 52 assessments will complete the 8 weeks of additional safety follow-up to complete involvement in the study.

After all randomised subjects have completed the 52-week double-blind period the database will be soft-locked, and the **primary analysis** will be performed, including the assessment of the primary, secondary, exploratory and safety objectives. This analysis will also encompass all available data collected after the 52-week time point. At this stage the Sponsor and Sponsor's delegate who are not directly involved in the management of sites will be unblinded to randomised treatment, but the subjects and investigators will remain blinded (single-blind). The **end of study analysis** will be performed after all subjects have completed the second year extension period, and the database will be locked. One interim analysis may be conducted after approximately 80% of subjects have completed the Week 52 visit or would have completed if they had not discontinued the study. CCI

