3.6.1 Adverse events

Adverse events experienced by the subjects will be collected throughout the entire study, including the second year extension period, and will be coded using the latest version of MedDRA.

Adverse event data will be categorised according to their onset date into the following study periods:

- AEs occurring during screening:
An AE during screening is defined as an AE with a date of onset \geq date of the screening visit and date and time of onset $<$ date and time of the first dose of IP.
AEs occurring during screening will only be listed.
- AEs occurring during treatment:
An AE during treatment is defined as an AE with a date and time of onset \geq date and time of first dose of IP and \leq date of last dose of IP + 28 days.
- AEs occurring during follow-up:
An AE during follow-up is defined as an AE with a date of onset $>$ date of last dose of IP + 28 days and \leq date of last dose of IP + 84 days.
- AEs occurring after follow-up:
An AE after follow-up is defined as an AE with a date of onset $>$ date of last dose of IP + 84 days.
AEs occurring after follow-up will only be listed.

If an AE has a missing onset date, then unless the stop date of the AE indicates otherwise, this will be considered as an AE during treatment. Similarly, if an AE has a partial onset date, then unless the partial onset date or the stop date indicates otherwise, this will be considered an AE during treatment.

Adverse events with missing intensity will be assumed to be severe. Events with missing relationship to study medication per the investigator will be assumed to be related. If no information about seriousness is available, the AE will be considered serious.

An acute AE is defined as an AE with a date of onset on any day of administration of IP and a time of onset on or after the start of administration of IP or a date of onset occurring on the subsequent day. If an AE has a missing onset date, then unless the stop date of the AE indicates otherwise, this will be considered as an acute AE. Similarly, if an AE has a partial onset date, then unless the partial onset date or the stop date indicates otherwise, this will be considered acute AE.

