Adverse events during treatment will also be presented by time intervals of the first onset of the event. For this analysis, repeated events with the same preferred term will not be considered (i.e. if a subject has more than one event with the same preferred term, only the event with the earliest date of onset will be used). For partial or missing dates, the rules as described above will be used. The following time intervals (defined as exact weeks, independent of the study visits and with no visit windowing) are defined:

- Day 1 to $<$ Week 12:
AEs with date of onset \geq date of first administration of IP and $<$ date of first administration of IP plus 84 days

- Week 12 to < Week 24:
AEs with date of onset \geq date of first administration of IP plus 84 days and < date of first administration of IP plus 168 days
- Week 24 to < Week 36:
AEs with date of onset \geq date of first administration of IP plus 168 days and < date of first administration of IP plus 252 days
- Week 36 to < Week 48:
AEs with date of onset \geq date of first administration of IP plus 252 days and < date of first administration of IP plus 336 days
- Week 48 to < Week 60:
AEs with date of onset \geq date of first administration of IP plus 336 days and < date of first administration of IP plus 420 days
- Week 60 to < Week 72:
AEs with date of onset \geq date of first administration of IP plus 420 days and < date of first administration of IP plus 504 days
- Week 72 to < Week 84:
AEs with date of onset \geq date of first administration of IP plus 504 days and < date of first administration of IP plus 588 days
- Week 84 to < Week 96:
AEs with date of onset \geq date of first administration of IP plus 588 days and < date of first administration of IP plus 672 days
- Week 96 to < Week 100:
AEs with date of onset \geq date of first administration of IP plus 672 days and < date of first administration of IP plus 756 days
- \geq Week 100:
AEs with date of onset \geq date of first administration of IP plus 756 days

The event rate per 100 subject years is defined as the number of subjects with an event divided by the sum of exposure time in days (e.g. date of last dose of IP + 28 days - day of first dose of IP + 1 day for summary of AEs during treatment) for all subjects in the analysis set multiplied by 365.25 days/year multiplied by 100.

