4.2.6.1 Adverse Events

If not stated otherwise, all summaries described below will be presented separately for

- AEs during treatment
- AEs during follow-up

For summaries during follow-up, only subjects with any study documentation after the date of last dose of IP + 28 days will be considered.

An overall summary of subjects with at least one AE in the following categories will be presented, and will include the event rate per 100 subject years, and total exposure in years for each treatment group:

- Any AE
- Any acute AEs
This category will not be included in the summary during follow-up.
- Any AE with outcome = death
- Any SAE (including events with outcome = death)
- Any AE leading to discontinuation of IP
 - This category will not be included in the summary during follow-up.
- Any AE related to IP by investigator's judgement
- Any AE of severe intensity
- Any AESI
 - Any AESI of non-opportunistic serious infections
 - Any AESI of opportunistic infections
 - Any AESI of anaphylaxis
 - Any AESI of malignancy
 - Any AESI of herpes zoster
 - Any AESI of tuberculosis
 - Any AESI of influenza
 - Any AESI of vasculitis (non-SLE)
 - Any AESI of major acute cardiovascular events (MACE as adjudicated)
- Any other significant AE

The number and percentage of subjects with at least one AE (i.e. multiple occurrences of an AE in 1 subject will only be counted once) will be summarised by MedDRA system organ class and preferred term (unless specified otherwise) for the following AE categories. These summaries will also include the event rate per 100 subject years and total exposure in years for each treatment group (unless specified otherwise).

- Any AE
- Any AE above reporting threshold of 2% of subjects in any treatment group in the full analysis set.
This summary will be presented by preferred term for AEs during treatment only.
- Any non-serious AE above reporting threshold of 5% of subjects in any treatment group in the full analysis set
This summary will not include the event rate per 100 subject years and total exposure in years.
- Any SAE with outcome = death
This summary will be presented for SAEs with an outcome of death during the treatment and follow-up periods combined.
- Any SAE (including events with outcome = death)
- Any AE leading to discontinuation of IP
This summary will be presented for AEs during treatment only.
- Any AE by relationship to IP (yes, no)

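### AE, SAE and AESI totals are summarised over up to two years of treatment with no 52-week cut, although Year-2 dosing depends on renal response and staying on IP, so the between-arm safety comparison can shift with efficacy

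*SAP*

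**What the plan says.** SAP 3.6.1 collects AEs over both years: "Adverse events experienced by the subjects will be collected throughout the entire study, including the second year extension period". It then assigns each AE to a study period. "An AE during treatment is defined as an AE with a date and time of onset" on or after first dose and no later than 28 days after last dose. Nothing divides that period at Week 52.

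SAP 4.2.6.1 introduces its tables with "If not stated otherwise, all summaries described below will be presented separately for" two periods, treatment and follow-up; Protocol 8.5.4 makes the same split. The overall summary "will include the event rate per 100 subject years, and total exposure in years for each treatment group". SAP 3.6.1 gives the rate: "The event rate per 100 subject years is defined as the number of subjects with an event divided by the sum of exposure time". The denominator is the exposure of every subject in the analysis set and is not stopped at a subject's first event. Under SAP 4.1.3, percentages use everyone in the analysis set by arm.

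Protocol 3.9.3 controls Year-2 dosing: "Subjects meeting the following criteria may continue to receive blinded IP between Weeks 52 and 100". The criteria are the eGFR and 24-hour UPCR parts of PRR, no discontinuation of IP, and a negative HIV test. SAP 1.2 says of the primary analysis: "This analysis will also encompass all available data collected after the 52-week time point".

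Three planned outputs bear on the point: a table of AEs by time interval of first onset (3.6.1, 4.2.6.1), a time-at-risk rate for herpes zoster that may be extended to other AESIs, and a Kaplan-Meier plot for herpes zoster.

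**The concern.** Exposure beyond Week 52 is earned by responding and by staying on IP. An effective drug therefore accumulates more exposure per randomised subject than placebo, for reasons unrelated to harm.

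The two planned measures react in opposite directions. The rate counts a subject once but keeps adding that subject's exposure after the event. For an AE that most subjects have already had, or that clusters in Year 1, an extension year adds a full year of denominator and little numerator, so the rate falls in the arm that continues more. The crude percentage rises in that arm, because its subjects are observed on treatment for longer.

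What is at stake is how a reader interprets the treatment and placebo columns of the main safety tables. The end-of-study tables carry the full effect. The primary-analysis tables carry part of it, because they include whatever Year-2 data exist by then.

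**Working it through.** The plan states no expected AE rate and no expected share continuing, so there is no figure of its own to reproduce. The check gives both arms the same AE risk and asks what the planned measures would show.

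**Exposure per subject (SAP 3.5.5: last dose + 28 days − first dose + 1).**
- Last dose at Week 48: 336 + 28 + 1 = 365 days.
- Last dose at Week 100: 700 + 28 + 1 = 729 days, about twice as much.

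**Share continuing.** From SAP 1.3: Week 52 to baseline UPCR ratios 0.35 and 0.54, SD of the log change 0.8. Assumed: baseline UPCR log-normal, median 2.5 to 3.5 mg/mg, log SD 0.5 to 0.6, truncated above 1 mg/mg as entry requires. Applying the Week 52 UPCR criteria (baseline ≤3: below 1.0; baseline >3: more than 50% fall and ≤3.0) by simulation gives 63-67% of anifrolumab and 43-47% of placebo subjects eligible. The eGFR criterion, early discontinuation and the Pap smear and QuantiFERON stops are not modelled. I use 65% and 45%.

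**Planned measures under identical risk.** Let c be the share continuing, p1 the Year-1 risk and p2 the Year-2 risk among continuers still event-free. Exposure is rounded to one and two years.
- Percentage = p1 + c(1 − p1)p2
- Rate = percentage / (1 + c)

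For p1 = 0.90 and p2 = 0.50: (0.90 + 0.65 × 0.10 × 0.50)/1.65 = 0.565 and (0.90 + 0.45 × 0.10 × 0.50)/1.45 = 0.636.

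For p1 = 0.10 and p2 = 0.03: (0.10 + 0.65 × 0.90 × 0.03)/1.65 = 0.071 and (0.10 + 0.45 × 0.90 × 0.03)/1.45 = 0.077.

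| Assumed risk, Year 1 then Year 2 | Percentage, anifrolumab v placebo | Ratio | Rate per 100 subject-years | Ratio |
|---|---|---|---|---|
| 90% then 50% | 93.25 v 92.25 | 1.01 | 56.5 v 63.6 | 0.89 |
| 10% then 3% | 11.8 v 11.2 | 1.05 | 7.1 v 7.7 | 0.92 |
| 10% then 10% | 15.85 v 14.05 | 1.13 | 9.6 v 9.7 | 0.99 |
| 5% then 5% | 8.1 v 7.1 | 1.13 | 4.9 v 4.9 | 1.00 |

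With no difference in risk, every ratio should be 1.

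**Second check, using hazards.** With first-event hazards λ1 and λ2 per year, Y1 = 365/365.25 and Y2 = 729/365.25:
- Percentage = (1 − c)(1 − exp(−λ1Y1)) + c(1 − exp(−λ1Y1 − λ2(Y2 − Y1)))
- Rate = percentage / [(1 − c)Y1 + cY2]

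Take 60% v 40% continuing and equal constant hazards. At 3 per year the rates are 61.3 v 69.3 (ratio 0.88). At 1 per year they are 48.3 v 51.8 (0.93). At 0.05 per year they are 4.8 v 4.8, while the percentages are 7.6 v 6.7 (1.14). A true hazard ratio of 1.2 at 1 per year appears as a rate ratio of 1.00. If the shares are reversed, so is the direction (1.13 at 3 per year). With equal shares the artefact vanishes.

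**Does stopping the clock at first event suffice?** On pooled data with constant hazard, yes: the ratio is 1.00. If the Year-2 hazard is half that of Year 1, the ratio is still 0.95 to 0.99 at 60% v 40%. With a Year-1 cut, both measures are equal between arms under equal hazards, apart from early discontinuation.

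**The case against.** Four arguments on the other side have force.

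- **The objective is descriptive.** A reader might infer that a formal safety comparison fails. The documents do not support that: the objective is to characterise safety and tolerability, the protocol synopsis calls for descriptive analysis, and no test rests on this rate. This limits the consequence to interpretation, but the tables still place arms side by side in a placebo-controlled trial.
- **The rate is not always wrong.** A reader might infer that an effective drug's event rates always look lower. For uncommon AEs with constant yearly risk they hardly move. The 0.89 belongs to the any-AE category, the least informative one, and the 0.92 needs risk to fall from 10% to 3%.
- **The interval table helps.** A reader might infer that it comes without exposure. That is not established: SAP 4.2.6.1 puts event rates and total exposure in its system organ class and preferred term summaries unless stated otherwise and does not exempt this table, though it does not say whether exposure is interval-specific. Its first four intervals (to before Week 48) lie inside Year 1 and give first-onset counts by preferred term free of extension entry. However, subjects cannot be added across terms to give AE, SAE or AESI totals, and the Week 48 to <60 interval straddles Week 52.
- **Herpes zoster is already covered.** The SAP defines a rate on time to first event and a Kaplan-Meier plot for it, and it is the identified infectious risk. For other AESIs that rate is optional, to be decided before unblinding; for overall AEs and SAEs it is not planned.

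These narrow the point. None of them supplies a Year-1 comparison of the totals.

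**Conclusion.** The point holds as a gap in descriptive safety reporting. There is no 52-week summary of AE, SAE and AESI totals, and the two-year summaries mix harm with the share of subjects who continued.

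Under identical risk and 65% v 45% continuing, the SAP rate is understated in the arm that continues more by about 8% to 11% for AEs that are very common or concentrated in Year 1. For uncommon AEs at constant yearly risk the rate is off by about 1% or less, and the crude percentage is overstated by about 13%. A real excess of a common AE could be hidden in the rate.

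The sizes rest on assumed baseline UPCR, AE risks and continuation shares; only the UPCR ratios and SD come from the plan. The direction depends on which arm continues more. The structural finding rests on the text alone.

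**What to change.** In SAP 3.6.1 and 4.2.6.1:

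- Make the main between-arm AE, SAE and AESI summaries cover a fixed window for all treated subjects, from first dose to the earlier of 364 days after first dose (Week 52) and last dose + 28 days. Do not end the window at the first extension infusion: Protocol 4.2.1.2 allows that as late as Week 60, so continuers would get up to about 8 more weeks than non-continuers.
- In these tables, end each subject's time at the first event of that type. This extends the herpes zoster time-at-risk definition in SAP 3.6.1 to the other summaries.
- Present Year-2 AEs separately for subjects who received extension IP, labelled as a response-selected group.
- Keep the pooled two-year tables as supportive.

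The cost is SAP wording and one more set of tables from dates already collected, with fewer events in each. Trial conduct does not change.

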3.5.5 Exposure of IP

The duration of exposure to the IP per subject is defined as the number of days between the start and the end dates of IP plus the dosing frequency time:

$$\text{Duration of exposure (days)} = (\text{Last dosing date} + 28 \text{ days}) - \text{first dosing date} + 1.$$

The total number of infusions will be counted per subject. Furthermore, the number of subjects with an infusion will be assessed in 4-weekly categories (i.e. 4 weeks, 8 weeks, 12 weeks, ..., 104 weeks).

The time to discontinuation of IP is the same as the duration of exposure.

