The time to first onset of herpes zoster during treatment will be derived as date of first onset of herpes zoster – date of first administration of IP + 1. AEs with an onset date before the date of first administration of IP and AEs with an onset after 28 days after the date of last administration of IP will not be considered for the time to first onset of herpes zoster during treatment. If a subject has no herpes zoster during treatment, the time to first onset will be censored at the date of last administration of IP + 28 days.

For herpes zoster, an alternative event rate per 100 subject years will be derived as the number of subjects with herpes zoster divided by the sum of time at risk in days for all subjects in the analysis set multiplied by 365.25 days/year multiplied by 100. The time at risk is defined as time (including start and end date) from start of period (e.g. date of first administration of IP for events during treatment) to the date of first event, discontinuation or completion of the

study, or the database extract date, whatever comes first. This alternative event rate may also be calculated for other AESIs if suggested by data. This will be discussed during the BDR meeting and the decision will be made before unblinding the data.

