(multiple occurrences of an AE in 1 subject will only be counted once as related if at least one AE is related and as not related if all occurrences are not related)
This summary will be presented for AEs during treatment only.
- Any AE by maximum intensity (mild, moderate, severe)
(i.e. multiple occurrences of an AE in 1 subject will only be counted once with the maximum intensity in this AE)
This summary will be presented for AEs during treatment only.
- Any AESI
This summary will not be presented by system organ class but by AESI category (non-opportunistic serious infections, opportunistic infections, anaphylaxis, malignancy, herpes zoster, tuberculosis, influenza and vasculitis [non- SLE]).
- Any other significant AE
This summary will be presented for AEs during treatment only.
- Any AE by time interval (as detailed in Section 3.6.1) for the first onset of event
This summary will be presented for AEs during treatment only.

Cardiovascular outcome events as determined by the Cardiovascular Event Adjudication Committee will be presented separately, summarising the number of AEs submitted for adjudication and the outcomes of the adjudication including MACE classification. Site reported cardiovascular AEs, cardiovascular SAEs and their corresponding adjudicated outcomes will be listed.

The time to first onset of herpes zoster during treatment will be presented as a Kaplan-Meier plot including the number of subjects at risk at each visit.

Furthermore, the alternative event rates per 100 subject years for herpes zoster (and possible other AESIs) will be summarised for events during screening, during treatment, and during follow-up. The total time at risk will also be presented.

An overall summary of subjects with AE's in pre-specified categories will also be presented by ADA category.

Key subject information for subjects with an AE with outcome of death, subjects with serious AEs, subjects with an AE leading to discontinuation of IP, subjects with cardiovascular events and subjects with AESIs, respectively, will be provided.

All AEs and AEs in ADA positive (at any time) subjects will be listed.

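### The time-at-risk rule for the alternative herpes zoster rate names no period end, so followed literally its during-treatment denominator counts off-treatment days (minor)

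*SAP*

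**What the plan says.** SAP 3.6.1 divides the number of subjects with herpes zoster by summed time at risk, start and end dates included. Time at risk runs "from start of period (e.g. date of first administration of IP for events during treatment) to the date of first event, discontinuation or completion". On the plain grammar those last two terms refer to taking part in the trial. The sentence then closes its list with "study, or the database extract date, whatever comes first". The same definition may be extended to other AESIs after blind data review.

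SAP 4.2.6.1 says that these alternative rates "will be summarised for events during screening, during treatment, and during follow-up".

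SAP 3.6.1 sets the periods. A treatment AE has its onset no later than last dose + 28 days. A follow-up AE has its onset after that and no later than "date of last dose of IP + 84 days". Two neighbouring rules do use the treatment bound: the standard event rate counts exposure as "date of last dose of IP + 28 days - day of first dose of IP + 1 day", and in the herpes zoster Kaplan-Meier analysis, for a subject without an event, "the time to first onset will be censored at the date of last administration of IP + 28 days".

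On screening, SAP 3.6.1 says "AEs occurring during screening will only be listed", whereas SAP 4.2.6.1 includes a screening rate.

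**The concern.** The numerator is tied to a period by SAP 4.2.6.1; the denominator, on its stated stop list, is not. The example in the rule illustrates only where a period starts. Subjects remain under observation after the treatment period closes. SAP 1.2 gives 12 weeks of safety follow-up after the last dose, and SAP 1.2.5 follows early IP stoppers to Week 52 or Week 104, or for at least 12 weeks. Taken literally, the during-treatment denominator therefore holds days on which no event can count.

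Herpes zoster is the identified risk named in Protocol 1.3, and this rate would stand beside the standard one. Two programmers could also produce different denominators, one following the list and the other importing the period end from earlier in the section.

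**Working it through.** The plan states no herpes zoster rate or time-at-risk total, so there is no figure to reproduce. The check is a day count for an event-free subject on scheduled days with no earlier database extract.

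**Inputs.** Study days from SAP Table 2: Week 0 = 1, Week 12 = 85, Week 24 = 169, Week 40 = 281, Week 44 = 309, Week 48 = 337, Week 52 = 365, Week 60 = 421, Week 100 = 701, Week 104 = 729, Week 112 = 784. Study exit is Week 60 or Week 112 for completers. For IP stoppers it is the later of Week 52 (or Week 104 in the extension) and last dose + 84 days.

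**Formulas**, with L the last dose day and E the exit day:
- as written: E − 1 + 1 = E
- bounded by the treatment period: (L + 28) − 1 + 1 = L + 28

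| Subject | L | E = days as written | L + 28 | Extra days |
|---|---|---|---|---|
| Completes Week 48, leaves at Week 60 | 337 | 421 | 365 | 56 |
| Completes the extension, leaves at Week 112 | 701 | 784 | 729 | 55 |
| Last dose Week 0 | 1 | 365 | 29 | 336 |
| Last dose Week 12 | 85 | 365 | 113 | 252 |
| Last dose Week 24 | 169 | 365 | 197 | 168 |
| Last dose Week 40 | 281 | 365 | 309 | 56 |
| Last dose Week 44 | 309 | 309 + 84 = 393 | 337 | 56 |
| Last dose Week 60 in the extension | 421 | 729 | 449 | 280 |

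For completers the excess is 56/365 = 15.3% and 55/729 = 7.5%. The second count is 55 because scheduled Day 784 is 83 days after Day 701.

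**Follow-up rate.** The period runs from L + 29 to L + 84, which is 84 − 28 = 56 days. Completers show no excess: Days 366 to 421 are 56 days, and Days 730 to 784 are 55. Year 1 stoppers followed to Week 52 range from Days 30 to 365 = 336 days (last dose Week 0) to Days 310 to 365 = 56 days (last dose Week 40).

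**Screening rate.** Time at risk would start at screening and, as written, would not stop at the first dose.

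**Reading discontinuation as discontinuation of IP.** SAP 3.5.5 says "The time to discontinuation of IP is the same as the duration of exposure", which places it at L + 28.
- Early IP stoppers: L + 28 on both counts, so the excess disappears.
- Extension completers: still 784 against 729.
- Follow-up time for early stoppers: it starts at L + 29 and stops at L + 28, so (L + 28) − (L + 29) + 1 = 0 days.

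**The case against.** The strongest reply is that the rule speaks of a period and so presupposes the periods already defined in the same section. A programmer who takes the numerator's window from there would probably take the denominator's as well. Read alone, the numerator is just as unbounded as the denominator, and the two then match. This fails on the text: SAP 4.2.6.1 ties the rate to events in each period, and the denominator has an explicit stop list that omits the period end. What stands is that a sensible programmer may supply the bound, so a wrong output is possible rather than certain.

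The second reply is the IP reading of discontinuation. It has force. With SAP 3.5.5 it removes the during-treatment excess for early IP stoppers. Arguably it does so for Week 48 completers who do not enter the extension too, since SAP 4.2.5.1 describes them as discontinuing IP after completing treatment. It does not help extension completers, and it leaves early stoppers with no follow-up time at risk. The grammar also favours leaving the study. SAP 4.2.1, writing for continuous endpoints, dates IP discontinuation at the last administration; applied here, that would stop treatment time too early instead.

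A reader might infer that the herpes zoster rate is understated by the percentages above, or by far more given the one-dose case. The documents do not support this. An event-free subject adds only denominator days, and neither document says how many subjects fall in each row. Nor do they support a claim of a biased arm comparison: that would need IP stopping or extension entry to differ by arm, and no such rates are given. Even the direction relative to the standard rate is not fixed at the primary analysis. The standard formula has no cap at the extract date and can count up to 28 unobserved days for a subject still on IP.

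On screening, SAP 4.2.6.1 can be read as a stated exception to the listing-only rule, so this is a wording check and not a contradiction.

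**Conclusion.** The rule is wrong as written, and the point is minor. The omission is certain. The day counts assume scheduled visits, planned follow-up, no herpes zoster event and no earlier extract, with discontinuation read as leaving the study. How much the reported rate would move depends on the mix of subjects and on how the rule is programmed, and cannot be determined from the documents. No hypothesis test uses this rate, and the standard rate and the Kaplan-Meier plot also cover herpes zoster, both with the treatment bound stated.

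**What to change.** In SAP 3.6.1:
- Add to the stop list the end of the respective period: first dose of IP for screening, last dose of IP + 28 days for treatment, last dose of IP + 84 days for follow-up.
- Start follow-up time at risk on the day after last dose + 28 days.
- State that the numerator counts only subjects with a first onset within that period.

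As a wording check, either state that the screening rate in SAP 4.2.6.1 is an exception to the listing-only rule in SAP 3.6.1, or drop that rate.

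The cost is a few phrases in two SAP sections. No new data are needed, and no efficacy analysis changes.
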